2. LIST OF ABBREVIATIONS

AF	Atrial fibrillation
AIS	Acute ischemic stroke
BI	Boehringer Ingelheim
CI	Confidence interval
CNSR	China National Stroke Registry
CRC	Clinical research coordinator
CRF	Case report form
CRO	Contract research organization
DM	Diabetes mellitus
DMRP	Data management and review plan
DTN	Door-to-needle time
EDC	Electronic data collection
████████	████████
ICH	Intracranial hemorrhage
IQR	Interquartile range
IS	Ischemic stroke
IV-rtPA	Intravenous recombinant plasminogen activator
IVT	Intravenous thrombolytics
MI	Myocardial infarction
MOH	Ministry of Health
MRA	Magnetic resonance angiography
MRI	Magnetic resonance imaging
mRS	Modified Rankin Scale
NCRCND	National Clinical Research Center for Neurological Diseases
NIHSS	National Institutes of Health Stroke Scale
NIS	Non-interventional study
OTT	Onset-to-treatment time
PRF	Paper-based registry form
SAH	Subarachnoid hemorrhage
SEAP	Statistical and epidemiological analysis plan
SD	Standard deviation
TIA	Transient ischemic attack

4. PURPOSE AND SCOPE

The purpose of this document is to provide a more technical and detailed elaboration of the principal features of the analysis described in the protocol, and to include detailed procedures for executing the statistical analysis of the data.

This SEAP assumes familiarity with the protocol, including protocol amendments (if presents) and its supplementary materials. In particular, the SEAP is based on the planned analysis specification as written in the protocol Section 9 “[Research Methods](#)”. Therefore, SEAP reviewers may consult the protocol for more background information on the study, e.g., on study rational and background, study objectives, study design and population, inclusion and exclusion criteria, definition of measurements, covariates and expected outcomes.

5. AMENDMENTS AND UPDATES

NA

6. RESEARCH QUESTION AND OBJECTIVE

Research Question:

Whether the quality of IV-rtPA treatment thrombolysis treatment has been improved with the continuous development of stroke centers and stroke care quality control networks supported by academic society and MOH during the last decade in China?

Primary Objectives:

- To investigate the temporal changes in the proportion of IV-rtPA treatment from 2007 to 2017 among intravenous thrombolytics (IVT) eligible patients and overall AIS patients in China;
- To investigate the temporal changes in IV-rtPA treatment time intervals from 2007 to 2017 among IV-rtPA treated patients in China.

Secondary Objectives:

- To describe the demographic and clinical characteristics of the IV-rtPA treated patients, IVT eligible patients and the overall AIS patients from the CNSR I to III.

7. RESEARCH METHODS

7.1 STUDY DESIGN

The Chinese treatment guideline for AIS was updated in 2010 where the recommended time window for intravenous recombinant plasminogen activator (IV-rtPA) treatment was extended from 3h since symptoms onset to 4.5h. Along with the development of stroke centers and stroke care quality control system, in order to understand the impact of these efforts on the clinical practices for AIS treatment in China, this study is designed to evaluate the temporal changes from 2007 to 2017, in the IV-rtPA treatment proportion and treatment time intervals of AIS patients.

This study is designed to be non-interventional and exploratory, while the 10-year time window was made possible by combining existing data from three cross-sectional surveys of AIS patients in China: CNSR I (2007-2008), II (2012-2013), and III (2015-2017).

Patients in each of the CNSR waves will be divided into 3 major groups respectively: (1) all AIS patients, (2) IVT-eligible patients (arrival within 2h & 3.5h since symptom onset and without documented absolute contraindication), and (3) IV-rtPA-treated patients (treatment within 3h & 4.5h since symptom onset). This stratification allows calculation and description of IV-rtPA treatment proportion and treatment time intervals across the 10-year window. Taken together the demographic and clinical characteristics data embedded in the CNSR studies, the analysis will help to answer the research question, and hope to provide understanding of the gap between clinical practice and guideline recommendation for acute phase stroke care, and to provide evidence linking minimized in-hospital delays for IV thrombolysis with improved AIS outcomes.

7.2 SETTING

This study will use AIS patient data from CNSR I to III, stretching across a 10-year time frame from 2007 to 2017. CNSR is a nationwide, prospective stroke registry where patients with acute cerebrovascular diseases were continuously enrolled for 8-12 month every 5-year since 2007.

[REDACTED]

[REDACTED]

CNSR I (2007-2008) was conducted in 131 sites across China, including 113 tertiary and 18 urban hospitals, all the included ischemic stroke (IS) patients were older than 18 and within 14 days of onset. CNSR II (2012-2013) was conducted in 219 hospitals nationwide, and all the included IS patients were older than 18 and within 7 days of onset. CNSR III (2015-2017) was conducted in 201 hospitals, AIS or TIA patients aged 18 years and older within 7 days of symptom onset were included.

STUDY POPULATION

All eligible patients from the CNSR I to III will be included. It was estimated that in CNSR I, II, and III, the number of total AIS patient is 12415, 19604, and 15204, respectively.

The study will analyze data for the following patient groups:

(1) All AIS patients (patient group A): the overall AIS patients aged 18-80 years who arrived at hospital within 7 days of symptom onset;

(2) IVT-eligible patients (patient groups B and B'):

Patient group B and B' are subsets of patient group A: AIS patients who arrived at hospital within 2h (patient group B) and 3.5h (patient group B') of symptom onset and with no documented absolute contraindications to IVT treatment;

(3) IV-rtPA-treated patients (patient groups C and C'):

Patient group C is a subgroup of patient group B, while patient group C' is a subset of patient group B': IVT-eligible patients who arrived at hospital within 2h of symptom onset and received IV-rtPA within 3h of symptom onset (patient group C) and those who arrived at hospital within 3.5h of symptom onset and received IV-rtPA within 4.5h of symptom onset (patient group C').

The flow of data selection for each of the three reporting patient groups is depicted in Figure 1 below.

[figure not shown]

Figure 1. Patient groups selected for the time-trend study

The in- and exclusion criteria for each of the reporting groups are listed below:

All AIS patients (patient group A)

Inclusion criteria:

1. Aged 18-80 years
2. Diagnosed with AIS on admission

Exclusion criteria:

1. Missing baseline data including age and gender
2. Diagnosed with intracranial hemorrhage (ICH), Transient Ischemic Attack (TIA), subarachnoid hemorrhage (SAH), or unspecific stroke
3. Arrived at hospital after 7 days of symptom onset

IVT-eligible patients (patient groups B and B')**Inclusion criteria:**

1. Met the in- and exclusion criteria of "all AIS patients" (Group A)
2. Arrived at hospital within 2h (patient group B) or 3.5h (patient group B') of symptom onset

Exclusion criteria:

1. Missing key data including
 - I. symptom onset time (or last known well time);
 - II. hospital arrival time;
 - III. whether received IVT treatment or not;
 - IV. the time of IVT treatment
2. Documented IVT absolute contraindications, according to the case report form (CRF) for each of CNSR

IVT Absolute Contraindications according to CRFs for each of CNSR:**For CNSR I:**

- Aged above 80 years;
- CT evidence of intracranial haemorrhage;
- CT evidence of early signs of large cerebral infarction;
- Concurrence of epileptic seizures during ischemic stroke;
- Have suffered a stroke or severe head injury in the past 3 months;
- Uncontrolled hypertension despite active treatment. Uncontrolled hypertension refers to systolic blood pressure > 185 mmHg or diastolic blood pressure > 110 mmHg, measured at least 10 minutes apart and repeated 3 times;
- Known haemorrhagic condition with significant bleeding disorder at onset or within the past 6 months;
- Acute pancreatitis or proven ulcerative gastrointestinal disease within 3 months;
- Recent invasive cardiopulmonary resuscitation or childbirth within 10 days. Non stress vascular puncture (such as subclavian vein or femoral vein puncture);
- Blood glucose < 50 mg/dl (2.7 mmol/l) or > 400 mg/dl (22.2 mmol/l);
- Platelet count < 105/mm³;
- Prothrombin time (PT) (international normalized ratio [INR]) > 1.5 or PT > 15 or activated partial thromboplastin time (APTT) > 40 sec.

For CNSR II and III:

- Uncontrolled hypertension despite active treatment. Uncontrolled hypertension refers to systolic blood pressure > 185 mmHg or diastolic blood pressure > 110 mmHg;
- Concurrence of epileptic seizures during ischemic stroke;
- Recent surgery or trauma within 15 days;

- Recent intracranial or spinal surgery, head trauma, or stroke within 3 months;
- Previous history of intracranial haemorrhage, aneurysm, vascular malformation, or brain tumour;
- Active visceral bleeding within 22 days;
- Platelet count <105/mm³, APTT (after heparin treatment) > 40 sec, PT > 15 or PT (INR) > 1.7, or known haemorrhagic condition/suspected subarachnoid haemorrhage;
- CT evidence of ICH, SAH, or signs of large infarction.

IV-rtPA-treated patients (patient groups C and C')Inclusion criteria:

1. Met the in- and exclusion criteria of “IVT-eligible patients”
2. Treated with IV-rtPA within 3h (patient group C) or 4.5h (patient group C') of symptom onset

Exclusion criteria:

1. Not received IVT
2. Received IVT other than rtPA
3. Treated with IV-rtPA after 3h (group C) or 4.5h (group C') of symptom onset
4. Received additional treatments with intra-arterial reperfusion or experimental therapies

7.3 STUDY VISITS

This study examines the time window from symptom onset to hospital arrival and IV-rtPA treatment time (i.e. whether and when IV-rtPA treatment is issued to IVT-eligible patients). This is a non-interventional study based on existing data from CNSR registry, and no new data are collected nor are new study visits.

8. VARIABLES

8.1 EXPOSURES

The study is descriptive in nature. It will not assess the association between any exposure and outcomes.

8.2 OUTCOMES

8.2.1 Primary outcomes

For all the three waves of CNSR, the following primary outcomes will be assessed:

- Proportion of patients who received IV-rtPA treatment within 3h of symptom onset (patient group C) among 2h IVT-eligible patients (patient group B);
- Proportion of patients who received IV-rtPA treatment within 4.5h of symptom onset (patient group C') among 3.5h IVT-eligible patients (patient group B').

8.2.2 Secondary outcomes

Among all AIS patients (patient group A) for all three waves of CNSR:

- Proportion of patients who arrived at hospital within 2h of symptom onset and who received IV-rtPA treatment within 3h of symptom onset (patient group C);
- Proportion of patients who arrived at hospital within 3.5h of symptom onset and who received IV-rtPA treatment within 4.5h of symptom onset (patient group C');

[figure not shown]
[figure not shown]
Among 3h IV-rtPA patients (patient group C) for all three waves of CNSR:

- The door-to-needle (DTN) time (time between arrival at hospital and the administration of IV-rtPA treatment);
- Proportion of patients DTN time \leq 60 minutes (min);
- Time between symptom onset and arrival at hospital;
- Time between symptom onset and the administration of IV-rtPA treatment.

Among 4.5h IV-rtPA patients (patient group C') for all three waves of CNSR:

- The DTN time;

- Proportion of patients DTN time \leq 60 min;
- Time between symptom onset and arrival at hospital;
- Time between symptom onset and the administration of IV-rtPA treatment.

9. DATA SOURCES

The current study will be conducted based on data collected from the three waves of CNSR, where patients with acute cerebrovascular diseases were enrolled every 5 year from 2007 till 2017.

CNSR I (2007-2008) used data from 131 sites across China, including 113 tertiary and 18 urban hospitals, all the included ischemic stroke (IS) patients were older than 18 and within 14 days of onset. Paper based registry forms (PRF) were used for data collection. Patient information including demographics (age, gender, etc.), NIHSS, medical history (diabetes mellitus, hypertension, coronary heart disease/previous myocardial infarction, atrial fibrillation, previous stroke, TIA, dyslipidemia), symptom onset to door time, health insurance schemes (urban basic medical insurance schemes for urban and governmental employees and urban residents, new rural cooperative medical schemes for rural residents, commercial insurance, and self-payment), vascular risk factors, imaging (mainly magnetic resonance imaging (MRI) or magnetic resonance angiography (MRA)), blood sampling, time related variables (symptom onset time, hospital arrival time, CT time, IV rtPA treatment time, etc.), implementation of performance measures for acute stroke care, final diagnosis, length of stay, in hospital death, and follow up information for 3 month, 6 month, and 12 month was collected. Hospital level information including geographic region (e.g., east, central, or west, according to the annual report on health statistics of China)), teaching status, hospital bed size, and annual stoke volume was collected.

CNSR II (2012-2013) used data from 219 hospitals in China, and all the included IS patients were older than 18 and within 7 days of onset. Web based case report forms (CRF) were used for data collection. Patient information including demographics, NIHSS, medical history, symptom onset to door time, health insurance schemes, vascular risk factors, imaging, blood sampling, time related variables, implementation of performance measures for acute stroke care, final diagnosis, length of stay, modified Rankin scale at discharge, and in hospital death was collected. Follow-up information for 3 month, 6 month, and 12-month was collected by phone interview. Hospital level information including geographic region, teaching status, hospital bed size, and annual stoke volume was collected.

CNSR III (2015-2017) used data from 201 hospitals in China, where AIS or TIA patients aged 18 years and older within 7 days of symptom onset were included for the study. An electronic data collection (EDC) system was used to collect data. Patient information including demographics, NIHSS, medical history, symptom onset to door time, health insurance schemes, vascular risk factors, imaging, blood sampling, time related variables, implementation of performance measures for acute stroke care, final diagnosis, length of stay, modified Rankin scale at discharge, and in hospital death was collected. Follow-up information for 3 month, 6 month, and 12 month was collected by phone interview. Hospital level information including geographic region, teaching status, hospital bed size, and annual stoke volume was collected.

10. DATA MANAGEMENT AND SOFTWARE/TOOLS

For this study, the data will be managed by the Data Management Group of NCRCND. Source code of data management and data analyses will be kept for inspection for at least five years after publication of the results.

10.1 SOFTWARE/TOOLS

Data management, tabulations, and graphics will be carried out with SAS version 9.4 software (SAS institute).

10.2 HANDLING OF MISSING VALUES

Every reasonable attempt have been undertaken to ensure completeness of data collection. In general, missing data will be treated as missing. No data imputation will be performed for the missing data. The amount of missing data will be reported and its effect on potentially bias conclusions will be assessed. Due to the nature of existing data, the interpretation is based on non-missing data.

10.3 HANDLING OF INCONSISTENCIES IN DATA AND QUTLIERs

Missing and erroneous values in patient cases can significantly impact the ability to perform research for identifying risk factors and disease distribution, treatment progression. This study is mainly based on review of data collected from CNSR I, II, III and aims at evaluating differences in clinical practice of IV-rtPA treatment among AIS patients from 2007 to 2017. Data follow-up period has already been finished. Thus, data cannot meet the criteria of this study will be excluded.

Exclusion criteria:

1. Missing key data including
 - symptom onset time (or last known well time);
 - hospital arrival time;
 - whether received IVT treatment or not;
 - the time of IVT treatment
 - age and gender
2. Contradiction of time period:
 - IVT treatment time earlier than symptom onset time (or last known well time);
 - treatment time earlier than hospital arrival time;
 - hospital arrival time earlier than symptom onset time
3. Diagnosed with intracranial hemorrhage (ICH), Transient Ischemic Attack (TIA), subarachnoid hemorrhage (SAH), or unspecific stroke
4. Arrived at hospital after 7 days of symptom onset

11. DATA ANALYSIS

The study is descriptive in nature. The calculation will be based on the available data.

For continuous data, descriptive statistics (number of patients, mean, standard deviation [SD], minimum, median, interquartile range, and maximum) will be presented. Categorical data will be presented as frequency and proportion with 95% CI as appropriate.

11.1 MAIN ANALYSIS

Patient group A includes patients aged 18-80 years and diagnosed with AIS on admission. Patients with missing baseline data including age and gender and diagnosed with intracranial hemorrhage (ICH), Transient Ischemic Attack (TIA), subarachnoid hemorrhage (SAH), or unspecific stroke and arrived at hospital after 7 days of symptom onset will be excluded.

Patient group B and patient group B' are both based on patient group A. And patients with missing key data will be excluded from patient group B and patient group B', including symptom onset time or last known well time, hospital arrival time, whether received IVT treatment or not and the time of IVT treatment.

Patients documented with IVT absolute contraindications, according to the case report form (CRF) for each of CNSR will be also excluded from patient group B and patient group B'.

Patients group B included patients who arrived at hospital within 2h of symptom onset.

[figure not shown]
Patients group B' included patients who arrived at hospital within 3.5h of symptom onset.

Patient group C is based on patients group B and patient group C' is based patient group B'. And both patient group C and patients group C' are to meet the inclusion criteria of "IVT-eligible patients". Patients not received IVT or received IVT other than rtPA or received additional treatments with intra-arterial reperfusion or experimental therapies will be excluded. Patients group C included patients who were treated with IV-rtPA within 3h. Patients group C' included patients who were treated with IV-rtPA within 4.5h.

11.1.1 Primary outcomes

For all the three waves of CNSR, the following primary outcomes will be assessed:([Table 1](#)
Proportion of 3 h IV-rtPA treatment among 2h IVT eligible patients & 4.5h IV-rtPA treatment among 3.5h IVT eligible patients)

- Proportion of patients who received IV-rtPA treatment within 3h of symptom onset (patient group C) among 2h IVT-eligible patients (patient group B);
- Proportion of patients who received IV-rtPA treatment within 4.5h of symptom onset (patient group C') among 3.5h IVT-eligible patients (patient group B').

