Till 2017, three waves of CNSR were completed: 2007-2008 (CNSR I), 2012-2013 (CNSR II), and 2015-2017 (CNSR III). The number of hospitals participating each of CNSR were 132, 219, and 201, respectively. When compared to CNSR I, data from CNSR II showed a 1.17-fold increase in the adjusted odds of delivering evidence-based performance metrics for ischemic stroke (IS) care. Nevertheless, no statistically significant difference in the proportion of patient who received intravenous thrombolytics (IVT) treatment within 3 hours (h) of symptom onset was observed between the two CNSR [P20-03289].

In China, IV-rtPA was approved for the treatment of AIS patients within 3h of symptom onset without absolute contraindications. However, in 2008, the European Cooperative Acute Stroke Study (ECASS) III study concluded that AIS patients could still benefit from IV-rtPA treatment when given between 3h and 4.5h [P08-12177]. The Chinese treatment guideline for AIS was updated in 2010, for which a recommendation of IV-rtPA treatment within 3h to 4.5h of symptom onset was added [P20-03291].

The current study aims at evaluating differences, if any, in clinical practice of IV-rtPA treatment among AIS patients from 2007 to 2017. In addition, the study will also provide information on the demographic and clinical characteristics of AIS patients receiving IV-rtPA in China. Taken together, the study will help us to better understand the trend of clinical practices for AIS treatment in China during the last decade, especially after the update of the

national AIS treatment guideline and the continuous efforts made by academic society and MOH in the field of stroke care.

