CNSR III (2015-2017) used AIS or TIA patient data from 201 hospitals in China. AIS or TIA patients aged 18 years and older within 7 days of symptom onset were included for the study. An electronic data collection (EDC) system was used through an electronic software or the internet. Patient information including demographics, NIHSS, medical history, symptom onset-to-door time, health insurance schemes, vascular risk factors, imaging, blood sampling, time-related variables, implementation of performance measures for acute stroke care, final diagnosis, length of stay, modified Rankin scale at discharge, and in-hospital death was collected. Follow-up information for 3-month, 6-month, and 12-month was collected by phone interview. Hospital-level information including geographic region, teaching status, hospital bed size, and annual stroke volume was collected.

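### The visible primary comparison is a crude C/B and C'/B' per wave, so a shift in arrival times within the eligible groups can move it with hospital practice unchanged

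*SAP*

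**What the plan says.** SAP 11.1.1 sets two primary outcomes per wave: "Proportion of patients who received IV-rtPA treatment within 3h of symptom onset (patient group C) among 2h IVT-eligible patients (patient group B"), and "Proportion of patients who received IV-rtPA treatment within 4.5h of symptom onset (patient group C') among 3.5h IVT-eligible patients (patient group B").

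The criteria under SAP 7.2 fix the two clocks. The denominator requires "Arrived at hospital within 2h (patient group B) or 3.5h (patient group B') of symptom onset"; the numerator requires "Treated with IV-rtPA within 3h (patient group C) or 4.5h (patient group C') of symptom onset". Both run from onset.

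The method in SAP 11 is "Categorical data will be presented as frequency and proportion with 95% CI as appropriate". Mock Table 1 has one n/N, % (95% CI) cell per wave and outcome, with no arrival band and no standardised row. Onset-to-door time appears in the visible tables only in Tables 3.2.1 and 3.2.2, which cover the treated groups C and C'.

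SAP 8.1 calls the study descriptive and says it will not assess associations. SAP 6 nevertheless poses the research question as "Whether the quality of IV-rtPA treatment thrombolysis treatment has been improved" with the development of stroke centres and quality-control networks. The limitations section (Protocol 9.9) covers data accuracy, missing data and hospital selection. It does not mention arrival time or patient mix.

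**The concern.** A patient who arrives 20 min after onset has 160 min in which to be treated and counted in C. One who arrives at 120 min has 60 min. The same hospital, with the same speed and the same willingness to treat, will put more of the first kind into the numerator. C/B and C'/B' therefore mix pre-hospital timing with in-hospital practice.

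If patients came earlier within the 2h or 3.5h window in a later wave, the crude proportion would rise and could be read as better hospital treatment. If they came later, a real improvement could be hidden. The visible tables would not show which had happened: treated patients are already selected for having arrived early enough, so their onset-to-door times do not describe B or B'.

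A shift in severity, age or sex could act in a similar way. The documents give no figures for this, so that part stays qualitative.

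**Working it through.** **1. The plan's own figures.** Protocol 9.5 assumes 4%, 5% and 28%. The Wald interval p ± 1.96·√(p(1−p)/N), with N = 14704, 19604 and 15204, gives 3.68-4.32%, 4.69-5.31% and 27.29-28.71%, which matches the stated intervals. These N are all AIS patients, not group B or B', so the intervals are narrower than the primary outcomes will have. The ratios to explain are 5/4 = 1.25 (CNSR I to II) and 28/5 = 5.6 (II to III).

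**2. Time left after arrival (no assumptions).**
- B: limit 180 min, arrival 0-120 min, so between 180 − 120 = 60 and nearly 180 min remain.
- B': limit 270 min, arrival 0-210 min, so between 270 − 210 = 60 and nearly 270 min remain.

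**3. Size for C/B (assumptions).** The documents give no arrival or door-to-needle (DTN) distribution. I assume:
- lognormal DTN with median m and log-SD s, the same in both waves and independent of arrival time;
- arrivals uniform within 15-60 min and within 60-120 min;
- a first-hour share that moves from 30% to 50%.

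P(in time | arrival a) = Φ((ln(180 − a) − ln m)/s). At m = 100 and s = 0.4 this is 84% for a = 30 and 10% for a = 120. Averaged over the bands it is 80.31% (early) and 39.22% (late).
- 30/70 mix: 0.3 × 80.31 + 0.7 × 39.22 = 51.55%
- 50/50 mix: 0.5 × 80.31 + 0.5 × 39.22 = 59.76%
- ratio: 59.76/51.55 = 1.16

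Any common share selected for treatment cancels from the ratio. With 40% selected, C/B goes from 20.6% to 23.9%.

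| Median DTN (min) | log-SD | 30/70 mix | 50/50 mix | Ratio | 4% would read |
|---|---|---|---|---|---|
| 45 | 0.4 | 95.28% | 96.55% | 1.01 | 4.05% |
| 45 | 0.6 | 89.09% | 91.37% | 1.03 | 4.10% |
| 60 | 0.4 | 85.86% | 89.39% | 1.04 | 4.16% |
| 60 | 0.6 | 78.73% | 82.57% | 1.05 | 4.20% |
| 80 | 0.4 | 68.75% | 75.35% | 1.10 | 4.38% |
| 80 | 0.6 | 64.20% | 69.50% | 1.08 | 4.33% |
| 100 | 0.4 | 51.55% | 59.76% | 1.16 | 4.64% |
| 100 | 0.6 | 51.11% | 57.02% | 1.12 | 4.46% |
| 120 | 0.4 | 37.09% | 45.31% | 1.22 | 4.89% |
| 120 | 0.6 | 40.26% | 46.15% | 1.15 | 4.59% |

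The reverse shift divides by the same ratio.

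**4. Larger shifts and C'/B'.** With Beta-shaped arrivals and median DTN 45-150 min:
- C/B, mean arrival 80 to 40 min: ×1.04-2.47. A smaller move, 60 to 40 min: ×1.02-1.43.
- C'/B', mean arrival 140 to 70 min: ×1.02-2.04. A smaller move, 105 to 70 min: ×1.01-1.33.

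A factor of 1.25 is within this range. A factor of 5.6 is not; the largest, 2.47, would take 5% to 12.4%.

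**5. Against sampling error.** If B is 10% of AIS patients (assumption; range 5-20%), CNSR I and II contribute about 1470 and 1960 patients. The 95% half-width for the difference is 1.96·√(0.04·0.96/1470 + 0.05·0.95/1960) = 1.4 points (2.0 to 1.0 over the range). The table's shifts on a 4% base are 0.05 to 0.89 points.

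**The case against.** **The adjustment may exist but be blacked out.** SAP numbering goes from 11.1 to 11.3 and the mock tables from Table 1 to Table 3.1. Redacted text follows Protocol 9.7.1, and 15 of the 22 rows of the variable dictionary are hidden. A reader might infer that no adjusted or stratified analysis is planned anywhere; the documents do not support that. What stands is narrower: the primary comparison, as visible, is crude.

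**Part of it is already covered.** A secondary objective is to describe the characteristics of the eligible groups, so case mix in B and B' should be reported in some form. The 2h/3h and 3.5h/4.5h pairing guarantees everyone at least 60 min. DTN time is reported per wave. These help, but they do not settle the point. The guaranteed minimum does not equalise the time left. DTN is seen only in patients treated before the limit, so it is itself cut off by arrival time.

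**The study is descriptive.** That is a fair reason to keep the crude proportion as primary. It does not cover a conclusion about treatment quality, which SAP 6 asks for.

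**The size is assumed.** This stands. Nothing in the documents shows that arrivals shifted, and at a median DTN of 60 min or less the effect is small. The modelled shift also lies within the sampling error of a CNSR I-II difference if B is about 10% of AIS patients, and Protocol 7 already reports no significant I-II difference in thrombolysis within 3h.

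**The adjusted precedent.** Protocol 7 states that "data from CNSR II showed a 1.17-fold increase in the adjusted odds of delivering evidence-based performance metrics". A reader might take this as the plan's own standard for C/B. It is background on a set of performance metrics, not a method for this outcome.

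**Conclusion.** The point holds for the visible primary comparison. That C/B and C'/B' depend on arrival time follows from the definitions and needs no assumption. Its size does: on the shift modelled, C/B is multiplied by about 1.01-1.05 at median DTN 45-60 min and by 1.08-1.22 at 80-120 min. The effect counts where the change between waves is small, as in the assumed 4% to 5%.

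Two stronger readings are tempting and unsupported. One is that earlier arrival could account for the assumed rise to 28%; no scenario came near the factor of 5.6, so arrival timing could distort the size of that rise but not create it. The other is that the crude comparison flatters the later waves; the direction is unknown, because later arrival would hide improvement. The case-mix part has no figures behind it.

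**What to change.** Keep crude C/B and C'/B' as the primary outcomes. Add to mock Table 1, for each wave:

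1. The distribution of onset-to-door time in B and in B'.
2. C/B by arrival band (0-1h, 1-2h) and C'/B' by arrival band (0-1h, 1-2h, 2-3h, 3-3.5h).
3. One supportive row per outcome, Σ w_k·p_k, where p_k is the wave's proportion in band k and w_k is that band's share of the pooled three-wave B or B'.

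If age, sex and NIHSS are also held fixed, use a logistic model with wave and these covariates, followed by marginal standardisation. Cell-wise direct standardisation would be too sparse. Two arrival bands, three NIHSS bands, three age bands and sex make 2 × 3 × 3 × 2 = 36 cells, while CNSR I would have about 0.04 × 1470 = 59 treated patients in B under the 10% assumption (29-118 over 5-20%).

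Add a sentence to SAP 11.1.1: the crude change reflects arrival timing as well as in-hospital practice and is to be read alongside the arrival-band and standardised rows. A pass/fail rule is not needed. If a redacted section already holds such an analysis, refer to it there.

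The cost is SAP wording and one extended table. Onset-to-arrival hours are in the visible variable dictionary. For the covariates, Protocol 9.4 lists for CNSR III "Patient information including demographics, NIHSS, medical history, symptom onset-to-door time", and the same items for the other two waves. The downsides are small band counts in CNSR I and II, and the loss of patients with missing NIHSS from any NIHSS-adjusted row; the arrival-only row avoids the second.
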